### **Assessment of Outcome**

The Investigator must judge outcome of the AE by the following terms:

- **Recovered/resolved:** The patient has fully recovered, or by medical or surgical treatment, the condition has returned to the level observed at the first trial-related activity after the patient signed the informed consent.
- **Recovering/resolving:** The condition is improving and the patient is expected to recover from the event. This term is only applicable if the patient has completed the trial or has died from another AE.
- **Recovered/resolved with sequelae:** The patient has recovered from the condition, but with lasting effect due to a disease, injury, treatment, or procedure. If a sequela meets an SAE criterion, the AE must be reported as an SAE.
- **Not recovered/not resolved**: The condition of the patient has not improved and the symptoms are unchanged, or the outcome is not known.
- Fatal: This term is only applicable if the patient died from a condition related to the reported AE. Outcomes of other reported AEs in a patient before he/she died should be assessed as "recovered/resolved", "recovering/resolving", "recovered/resolved with sequelae", or "not recovered/not resolved". An AE with fatal outcome must be reported as an SAE.
- **Unknown**: This term is only applicable if the patient is lost to follow-up.

# Follow-up of AEs and SAEs

- The Investigator is obligated to perform or arrange for the conduct of supplemental measurements and/or evaluations as medically indicated or as requested by Pharmalex to elucidate the nature and/or causality of the AE or SAE as fully as possible. This may include additional laboratory tests or investigations, histopathological examinations, or consultation with other health care professionals. The SAE follow-up information should only include new (e.g., corrections or additional) information and must be reported to Pharmalex within 24 hours of the Investigator's first knowledge of the information. This is also the case for previous non-serious AEs which subsequently become SAEs.
- If a patient dies during participation in the trial or during a recognized follow-up period, the Investigator will provide Pharmalex with a copy of any post-mortem findings including histopathology.
- New or updated information will be recorded in the originally completed eCRF.

# 10.3.4 Reporting of SAEs

# SAE Reporting to Pharmalex via the eCRF

- The primary mechanism for reporting an SAE to Pharmalex will be the eCRF.
- If the electronic system is unavailable, then the site will use the SAE paper form (see below) in order to report the event within 24 hours.
- The site will enter the SAE data into the electronic system as soon as it becomes available.
- After the trial is completed, the eCRF will be taken off-line to prevent the entry of new data or changes to existing data.
- If the trial site receives a report of a new SAE from a trial patient or receives updated data on a previously reported SAE after the eCRF has been taken off-line, then the site can report this information on a paper SAE form (see next section).

Reporting to Pharmalex via Paper CRF (in case of eCRF unavailability).

- SAE paper forms must be forwarded to Pharmalex.
- Email transmission of the SAE paper form is the preferred method to transmit this information to Pharmalex.
- Contact details for Pharmalex are:

[contact]

Email: [contact]

# **10.4** Appendix 4: Contraceptive Guidance and Collection of Pregnancy Information

# **Definitions:**

# Woman of Childbearing Potential (WOCBP)

A woman is considered fertile following menarche and until becoming postmenopausal unless permanently sterile (see below).

If fertility is unclear (e.g., amenorrhea in adolescents or athletes) and a menstrual cycle cannot be confirmed before first dose of trial intervention, additional evaluation should be considered.

# Females in the Following Categories Are Not Considered WOCBP

- 1. Premenopausal female with 1 of the following:
  - Documented hysterectomy
  - Documented bilateral salpingectomy
  - Documented bilateral oophorectomy

Females with permanent infertility due to an alternate medical cause other than the above, (e.g., Müllerian agenesis, androgen insensitivity), Investigator discretion should be applied to determining trial entry.

Note: Documentation can come from the site personnel's: review of the patient's medical records, medical examination, or medical history interview.

# 2. Postmenopausal female

- A postmenopausal state is defined as amenorrhea for 12 months without an alternative medical cause.
- A high FSH level (>25,8 IU/L) in the postmenopausal range may be used to confirm a postmenopausal state in women not using hormonal contraception or hormonal replacement therapy (HRT). However, in the absence of 12 months of amenorrhea, confirmation with more than one FSH measurement is required.
- Females on HRT and whose menopausal status is in doubt will be required to use one of the non-estrogen hormonal highly effective contraception methods if they wish to continue their HRT during the trial. Otherwise, they must discontinue HRT to allow confirmation of postmenopausal status before trial enrollment.

### **Contraception Guidance:**

### Female patients:

Highly effective contraception is defined as:

- Having a male partner who is sterile (vasectomized or orchiectomized) prior to the female patient's entry into the trial and is the sole sexual partner for that female patient.
- Use of intrauterine devices.
- Use of intrauterine hormone-releasing system.
- Bilateral tubal occlusion.
- Use of hormonal contraceptives containing combined estrogen and progestogen associated with inhibition of ovulation (intravaginal, transdermal).

- Use of progestogen-only hormonal contraception associated with inhibition of ovulation (injectable, implantable).
- True abstinence: When this is in line with the preferred and usual lifestyle of the patient (period abstinence [e.g. calendar, ovulation, symptothermal, post-ovulation methods] and withdrawal are not acceptable methods of contraception).

# Male patients:

Male patients who are not sterilized or infertile must use condom throughout the trial through 4 weeks after receiving the last trial product dose. If their partner is a female of childbearing potential, she must use highly effective contraception (as detailed above) throughout the trial through 4 weeks after last dose.

# **Collection of Pregnancy Information**

# Female patients who become pregnant

- The Investigator will collect pregnancy information on any female patient who becomes pregnant while participating in this trial.
- Female patients must be instructed to notify the Investigator immediately if she becomes pregnant or if she suspects she might be pregnant during the trial.
- All initial reports of pregnancy in female patients must be reported to PharmaLex by the trial site personnel within 24 hours of knowledge of the event using the appropriate pregnancy form.
- The initial information will be recorded on the appropriate form and submitted to the Sponsor within 24-hours of learning of a patient's pregnancy.
- The patient will be followed to determine the outcome of the pregnancy. The Investigator will collect follow-up information on the patient and the neonate, and the information will be forwarded to the Sponsor. Follow-up will not be required for longer than 1 month beyond the estimated delivery date. Any termination of pregnancy will be reported, regardless of fetal status (presence or absence of anomalies) or indication for the procedure.
- While pregnancy itself is not considered to be an AE or SAE, any pregnancy complication or elective termination of a pregnancy for medical reasons will be reported as an AE or SAE.
- Abnormal pregnancy outcomes (e.g. spontaneous abortion [occurring at <22 weeks gestational age], stillbirth [occurring at >22 weeks gestational age], fetal death, congenital anomalies, and ectopic pregnancy) are considered SAEs and must be reported using the SAE form.
- Any post-trial pregnancy related SAE considered reasonably related to the trial intervention by the Investigator will be reported to the Sponsor as described in Section 8.4.1. While the Investigator is not obligated to actively seek this information in former trial patients, he or she may learn of an SAE through spontaneous reporting.
- Any female patient who becomes pregnant while participating in the trial will discontinue trial intervention.

### Male patients with partners who become pregnant

- Because the effect of the trial product on sperm is unknown, the Investigator will attempt to collect pregnancy information on any male patient's female partner who becomes pregnant while the male patient is in this trial. This information will include medical history in relation to previous pregnancy(ies) and birth(s), if applicable, relevant medical history, and information on present pregnancy.
- Male patients must be instructed to notify the Investigator immediately if his partner becomes pregnant or suspects to be pregnant.
- After obtaining the necessary signed informed consent from the pregnant female partner directly, the Investigator will record pregnancy information on the appropriate form and submit it to PharmaLex within 24-hours of learning of the partner's pregnancy. The female partner will also be followed to determine the outcome of the pregnancy. Information on the status of the mother and child will be forwarded to the Sponsor. Generally, the follow-up will be no longer than 1 month following the estimated delivery date. Any termination of the pregnancy will be reported regardless of fetal status (presence or absence of anomalies) or indication for the procedure.

# 10.5 Appendix 5: Abbreviations

| ADA              | anti-drug antibody                          |
|------------------|---|
| AE               | adverse event                               |
| AESI             | adverse event of special interest           |
| ALP              | alkaline phosphatase                        |
| ALT              | alanine aminotransferase                    |
| AST              | aspartate aminotransferase                  |
| AUC              | area under the curve                        |
| BMI              | body mass index                             |
| CA               | competent authority                         |
| CCE              | colon capsule endoscopy                     |
| CLcr             | creatinine clearance                        |
| C max | maximum plasma concentration                |
| CONSORT          | Consolidated Standards of Reporting Trials  |
| CRF              | case report form                            |
| CT               | computerized tomography                     |
| CTR              | clinical trial report                       |
| DEXA             | dual-energy x-ray absorptiometry            |
| DILI             | drug-induced liver injury                   |
| DMC              | data monitoring committee                   |
| DPP              | dipeptidyl peptidase                        |
| ECG              | electrocardiogram                           |
| eCRF             | electronic case report form                 |
| eGFR             | estimated glomerular filtration rate        |
| EMA              | European Medicines Agency                   |
| ЕоТ              | end of treatment                            |
| FAS              | full analysis set                           |
| FDA              | US Food and Drug Administration             |
| FDAAA            | Food and Drug Administration Amendments Act |
| FSH              | follicle-stimulating hormone                |
| FU               | follow-up                                   |
| GGT              | gamma-glutamyl transferase                  |

| GLP-2  | glucagon-like peptide 2  |
|--------|--|
| HbA1c  | hemoglobin A1c   |
| HGH    | human growth hormone   |
| HIV    | human immunodeficiency virus   |
| HRT    | hormone replacement therapy  |
| IBD    | inflammatory bowel disease   |
| ICF    | informed consent form  |
| ICH    | International Council for Harmonisation                                      |
| IEC    | independent ethics committee   |
| INR    | international normalized ratio   |
| MDRD   | modification of diet in renal disease  |
| MedDRA | Medical Dictionary for Regulatory Activities                                 |
| MRI    | magnetic resonance imaging   |
| NOAEL  | no observed adverse-effect level   |
| NYHA   | New York Heart Association   |
| PCD    | primary completion date  |
| PGIC   | patient's global impression of change  |
| PK     | pharmacokinetics   |
| PRO    | patient reported outcome   |
| PS     | parenteral support   |
| SAE    | serious adverse event  |
| SAP    | statistical analysis plan  |
| SAS    | safety analysis set  |
| SBS    | short bowel syndrome   |
| SBS-I  | SBS impact scale (a disease specific PRO questionnaire developed by Sponsor) |
| SBS-IF | short bowel syndrome with intestinal failure                                 |
| SBS-II | short bowel syndrome with intestinal insufficiency                           |
| SC     | subcutaneous   |
| SD     | standard deviation   |
| SUSAR  | suspected unexpected serious adverse reaction                                |
| ULN    | upper limit of normal  |
| WOCBP  | woman of childbearing potential  |

1 GENERAL

This Statistical Analysis Plan (SAP) specifies the statistical methods to be applied in the final analysis of this study. It was written by the responsible biostatistician prior to database lock.

This SAP Plan is based upon the Study Protocol (version 2.0 of 18Feb2021) and Protocol Amendment (version 3.0 of 02Jul2021) and contains a specification of the statistical methods described therein. The analysis will be performed according to Standard Operating Procedures (SOPs) of KLIFO.

The primary objective of this phase 3b study is to demonstrate the 24-week effect of glepaglutide on the absorption of fluids.

For this purpose, this trial has been designed as a single-center, single-arm, fixed dose, phase 3b trial to investigate the long-term effect on intestinal absorption and nutritional status and to assess long-term safety of treatment with glepaglutide in patients with Short Bowel Syndrome (SBS).

All patients will receive the same treatment.

The primary endpoint is the change from baseline to Week 24 in the absorption of wet weight/fluids as assessed by 48-hour metabolic balance studies.

The study phase for an individual patient consists of a screening period of up to 3 weeks, a treatment period of 52 weeks, during which all trial patients will receive treatment of glepaglutide, and a follow-up period of 4 weeks.

A total of 14 visits are scheduled:

Screening visit (SCR): Up to 21 days before V1,
Baseline visit (V1): Day -3 to Day 1 (Week 0),
Ten visits (V2-V11): Week 1 to Week 40,

End of treatment (EOT) / Withdrawal visit (V12): Week 52,

Follow-up visit (FU): Week 56.

2 EFFICACY AND SAFETY VARIABLES

2.1 General procedures

2.1.1 Time definitions and handling of visits

2.1.1.1 Scheduled visits

A total of 14 visits with investigations are planned.

For all patients who withdraw from the trial, a withdrawal visit should be carried out. The withdrawal visit has to be conducted as a Week 52 end of treatment (EOT) examination and documented in the electronic case report form (eCRF).

Details on the scheduled visits and how they will be presented in the analysis are shown in the table below.

Visit	Scheduled for / as	Documented in eCRF as Visit	Presented in this Analysis as Visit
Screening (SCR)	Up to 21 days before V1	SCR	Screening
Baseline (V1)	Day -3 to day 1 (W0)	Visit 1 – Week 0 – [Day 1 – Day 4] ^{\$}	Baseline &
Visit (V2)	Week 1	Visit 2 – Week 1	Week 1
Visit (V3)	Week 2	Visit 3 – Week 2	Week 2
Visit (V4)	Week 4	Visit 4 – Week 4	Week 4
Visit (V5)	Week 8	Visit 5 – Week 8	Week 8
Visit (V6)	Week 12	Visit 6 – Week 12	Week 12
Visit (V7)	Week 16	Visit 7 – Week 16	Week 16
Visit (V8)	Week 20	Visit 8 – Week 20	Week 20
Visit (V9)	Week 24	Visit 9 – Week 24 – [Day 1 – Day 4] ^{\$}	Week 24 &
Visit (V10)	Week 32	Visit 10 – Week 32	Week 32
Visit (V11)	Week 40	Visit 11 – Week 40	Week 40
EOT visit	Week 52 (completers)	EOT – Visit 12 – Week 52	Week 52
(V12)			ЕОТ
EOT visit (V12)	EOT (non-completers)	EOT – Visit 12 – Week 52	ЕОТ
Follow-up (FU)	Week 56	Follow-up Visit	Follow-up

Data at this visit will be collected over a period of 4 days (documented in the eCRF as Day 1, Day 2, Day 3, and Day 4) which includes a 48-hour Metabolic Balance Study (MBS).

This means, variables will in general be analyzed according to the visit as documented in the eCRF. Variables documented in the eCRF at visit 'EOT – Visit 12 – Week 52' will be presented in summary tables at visit 'EOT'. Values documented at this visit for completers will in addition be presented in summary tables at visit 'Week 52'. Whenever the subsequent text states that a variable or change will be summarized at 'Week 52 (EOT)', then this means it will be summarized at 'Week 52' (completers only) and separately at 'EOT' (all patients).

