#### 4.4 End of Trial Definition

A patient is considered to have completed the trial when he or she has completed trial product treatment for 52 weeks and completed both metabolic balance study periods (at Visit 1 and 9) as well as the final safety assessments at Visit 12 and completed the follow-up visit (week 56).

The end of the trial is defined as the date of the last visit (follow-up visit) of the last patient in the trial.

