### 7 DISCONTINUATION OF TRIAL PRODUCT AND PATIENT WITHDRAWAL

### 7.1 Discontinuation of Trial Treatment

Treatment of a patient may be discontinued at any time during the trial at the discretion of the Investigator for safety reasons. However, the patient can still continue, and should be encouraged to stay in the trial if assessed safe according to the Investigator.

Efforts must be made so that patients continue to attend and complete all scheduled visit procedures to the extent possible. Patients should stay in the trial regardless of compliance with trial drug, assessments, or visit schedule. The Investigators should make a special effort to ensure that all patients complete the assessment for the primary and key secondary endpoints.

Patients must be educated about the continued scientific importance of their data, even if they discontinue trial product.

A patient must be discontinued from trial treatment if:

- 1. Any safety concerns or AEs that in the opinion of the Investigator might place the patient at unacceptable risk, including any deterioration of a patient's health state, especially in terms of the frequency and volume of total PS.
- 2. Any malignancy.
- 3. Increased liver values, defined as:
  - a. ALT or AST >3 times baseline value lasting more than 2 weeks\*, or
  - b. ALT or AST  $>5 \times$  ULN and total bilirubin  $>2 \times$  ULN\*, or
  - c. ALT or AST  $>5 \times$  ULN and international normalized ratio (INR) >1.5\*, or
  - d. ALT or AST  $>5 \times$  ULN with the appearance of fatigue, nausea, vomiting, right upper quadrant pain or tenderness, fever, rash, and/or eosinophilia (>5%)\*
  - \* where no other etiology exists.
- 4. Pregnancy or intention to become pregnant.
- 5. The patient requires treatment with prohibited medications (see Section 6.6).

Patients can be discontinued from trial treatment if:

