• A patient was enrolled despite it was later identified that some of the inclusion or exclusion criteria were violated. The Investigator must discuss with the Sponsor's Medical Monitor if it is safe for the patient to continue the trial treatment. If a patient prematurely discontinues trial treatment, the primary reason must be specified in the eCRF. If the patient continues in the trial without trial treatment, the intent should be to follow the patient to the extent possible according to the planned visit schedule and assessments with the purpose of following the safety and efficacy of the patients. Reason for visits not having been performed must be documented.

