4.2.2 Protocol Deviations

The following protocol deviations will be tabulated:

- Violation of inclusion/exclusion criteria
- Compliance with time window for Week 52 (EOT): Difference between date of baseline visit date and date of Week 52 (EOT) within or outside the allowed window, for patients who completed the treatment phase.

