9 APPENDICES

- A List of Summary Tables
- B List of Data Listings
- C List of Figures
- D Modifications of Summary Tables and Data Listings for Interim Analysis

List of Summary Tables

Analysis Sets:

ALL = All Patients Included into the Trial

FAS = Full Analysis Set

PPS = Per-Protocol Set

SAS = Safety Analysis Set (Note: if FAS=SAS, then FAS will be used)

No.	Title/Content	Analysis Sets				
1. Study Pati	1. Study Patients					
1-1.1	Number of patients screened and included in each analysis set	ALL				
1-1.2	Reasons for exclusion from per-protocol analysis set	FAS				
1-1.3	Study completion: Completion of treatment phase and reasons for premature discontinuation	FAS				
1-1.4	Treatment duration: Duration of trial product administration during treatment phase	FAS				
1-1.5.1	Study duration: Last visit during treatment phase	FAS				
1-1.5.2	Study duration: Follow-up visit performed	FAS				
1-2.1	Inclusion criteria	FAS				
1-2.2	Exclusion criteria	FAS				
1-2.3.1	Protocol violations - Overview	FAS				
1-2.3.2	Protocol violations - Details	FAS				
1-2.4	Compliance with time window for Week 52 (EOT) for completers	FAS				
1-3.1	Demographic data: Sex, age, race, ethnicity, body height and weight	FAS / PPS				
1-3.2.1	SBS characteristics and history: Type, cause and severity of SBS, time since diagnosis of underlying disease, time since SBS diagnosis	FAS / PPS				
1-3.2.2	SBS characteristics and history: Time since most recent resection, reason for resection	FAS / PPS				
1-3.2.3	SBS characteristics and history - Remaining bowel sections - Colon-in-continuity (including type) - End-jejunostomy/SBS anatomical group 1 - Ileostomy/SBS anatomical group 1 - Colostomy - Presence of ileocecal valve	FAS				

No.	Title/Content	Analysis Sets
1-3.2.4	SBS characteristics and history - Bowel lengths - Length of the remnant small bowel - Remnant colon in percent	FAS
1-3.2.5	SBS characteristics and history: Time since start of PS (if applicable)	FAS
1-3.3	Medical history/concomitant illness - Encephalopathy - Ascites - Cholestasis - Steatosis - Cirrhosis	FAS
1-3.4	Baseline characteristics: Substance abuse - Alcohol abuse - Drug abuse - Tobacco smoking	FAS
1-4	Drug exposure and treatment compliance	FAS / PPS
1-5.1	Pre-treatment therapies	FAS
1-5.2	Concomitant therapies commenced or ongoing at date of first administration of trial product	FAS
1-5.3	Concomitant therapies commenced after date of first administration of trial product	FAS

No.	Title/Content	Analysis Sets	

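### SAP 2.1.1.1 limits the 'Week 52' row to treatment completers, so off-drug patients' Week 52 values appear only under 'EOT', which mixes time points once anyone withdraws early

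*SAP*

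**What the plan says.** SAP 2.1.1.1 maps eCRF visits to analysis visits. Visits 6 and 9 map straight to Week 12 and Week 24 for every patient with that visit. Visit 12 is split. All its records go to 'EOT', and then "Values documented at this visit for completers will in addition be presented in summary tables at visit" 'Week 52'. The section adds that any later mention of 'Week 52 (EOT)' means both rows: 'Week 52' ("completers only) and separately at" 'EOT' for all patients.

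For patients who leave the trial, "The withdrawal visit has to be conducted as a Week 52 end of treatment (EOT) examination". A withdrawal visit at any week is therefore documented as the Week 52 visit and enters the 'EOT' row.

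Section 2.1.1.1 does not define completers. Other places point to treatment completion:

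- SAP 4.2.2 describes the Week 52 window check as being "for patients who completed the treatment phase". Appendix A titles the same check, table 1-2.4, "Compliance with time window for Week 52 (EOT) for completers".
- Listing 1-3.1 in Appendix B places that check with the Treatment Completion Status form. Completion of the full study is a separate listing, 1-3.2.
- Protocol 4.4, which defines completing the trial, includes having "completed trial product treatment for 52 weeks".

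Protocol 7.1 encourages patients who stop trial product to stay: "If the patient continues in the trial without trial treatment, the intent should be to follow the patient to the extent possible" on the planned visits and assessments. Protocol 7.2 counts only withdrawal of consent as withdrawal from the trial.

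**The concern.** A patient who stops trial product but attends Visit 12 at Week 52 is not a treatment completer. Under SAP 2.1.1.1 that patient's Week 52 measurement does not enter the 'Week 52' row.

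The filter is unlikely to be unrelated to outcome. Protocol 7.1 requires treatment to stop for safety concerns, including deterioration "especially in terms of the frequency and volume of total PS". PS volume, PS content and weekly days on PS are themselves Week 52 endpoints. A row restricted to patients who stayed on drug therefore tends to leave out those who did worse on these variables.

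The protocol's Week 52 endpoints carry no completer condition. SAP 4.3.4 analyses exploratory endpoints on the FAS, Appendix A labels the Week 52 efficacy tables FAS (some also PPS), and SAP section 6 does not list the restriction among the changes from protocol. Someone comparing Week 12, Week 24 and Week 52 in one table would be comparing different kinds of population.

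**Working it through.** The plan states no figure on this point, so there is nothing to reproduce. The check is a head count of who falls in which row.

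**Inputs**

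- N, patients treated: 10 planned (protocol 9.2), with a range of 6 to 16 (protocol 4.1).
- a, patients who stop trial product but attend Visit 12 at Week 52: assumed.
- w, patients who leave before Week 52 and have a withdrawal visit recorded as Visit 12: assumed.
- Also assumed: each treated patient has one Visit 12 record, and for the a patients it is filled in at Week 52.

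**Formulas, from SAP 2.1.1.1**

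- 'Week 52' row: N − a − w
- 'EOT' row: N
- Patients with a true Week 52 value: N − w

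| N | a | w | 'Week 52' row | 'EOT' row | True Week 52 value | Row that matches |
|---|---|---|---|---|---|---|
| 10 | 0 | 1 | 9 | 10 | 9 | 'Week 52' |
| 10 | 1 | 0 | 9 | 10 | 10 | 'EOT' |
| 10 | 1 | 1 | 8 | 10 | 9 | neither |
| 10 | 2 | 1 | 7 | 10 | 9 | neither |
| 10 | 1 | 2 | 7 | 10 | 8 | neither |
| 6 | 1 | 1 | 4 | 6 | 5 | neither |
| 16 | 1 | 1 | 14 | 16 | 15 | neither |

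If a = 0, the 'Week 52' row is the wanted set. If w = 0, the 'EOT' row is. If both are at least 1, neither row is.

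**Effect on a mean.** With c = N − a − w completers, the completer mean differs from the mean of all patients with a Week 52 value by

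a/(c + a) × (completer mean − off-drug mean).

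With a = 1 and w = 1 this fraction is 1/9 for N = 10 (c = 8), 1/5 for N = 6 (c = 4) and 1/15 for N = 16 (c = 14). For SBS-IF endpoints, take half the patients, in line with the planned equal split. The fraction is then 1/4 for 5 patients (c = 3), 1/2 for 3 patients (c = 1) and 1/7 for 8 patients (c = 6).

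**Illustration with invented values.** Take five SBS-IF patients and change in weekly PS volume: three completers at −4 L, one off-drug attender at +2 L, and one early leaver at 0 L.

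- 'Week 52' row: −4.0 L
- 'EOT' row: (3 × −4 + 2 + 0)/5 = −2.0 L
- All with a Week 52 value: (3 × −4 + 2)/4 = −2.5 L

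The gap of 1.5 L is 1/4 of the 6 L difference, as the formula gives. These values show the mechanism only and do not predict the trial's results.

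**The case against.** Several points on the other side stand.

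- **The rule is open.** SAP 2.1.1.1 states which row is completers and which is all patients. The continuous tables print valid n and missing n, table 1-1.3 gives completion and reasons for discontinuation, and listings 1-3.1 and 1-5 allow reconstruction from completion status and visit dates. A reader might infer that the restriction is hidden or that data are dropped; the documents do not support that. The off-drug values are pooled under 'EOT'. A falling n does not, however, tell a table reader that treatment completion is the cause.
- **The gap is conditional.** A reader might infer that no table can ever show Week 52 for all patients with a Week 52 value. That fails whenever nobody leaves early, because 'EOT' is then exactly that set, or whenever nobody stops drug and stays.
- **The meaning of completers is an inference.** If the word meant patients who attended Visit 12 at Week 52, the gap would close. SAP 4.2.2, table 1-2.4 and listing 1-3.1 make treatment completion the better reading, but the term needs a definition.
- **SAP 4.3.1 points the other way.** It says collection of treatment-phase data ends after withdrawal from the treatment phase, so there would be no off-drug Week 52 value to place. This conflicts with protocol 7.1. The SAP also does not say whether Visit 12 is filled in when drug stops or at Week 52 for a patient who stays. Protocol 8.3.6 asks for antibody sampling at end of treatment and about four weeks later, which leaves the timing open.
- **The stakes are limited.** Completers plus last assessment is a familiar two-row presentation. The metabolic balance studies are done only at baseline and Week 24, so their novelty lends no weight to Week 52.

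**Conclusion.** The point holds as a defect in the definition of an analysis visit. If completers are treatment completers, as the SAP's own cross-references indicate, the 'Week 52' row is a completer-selected summary inside tables labelled FAS, and the selection can depend on the outcome. When at least one patient stops drug but attends Week 52 and at least one other has an early withdrawal visit, the plan has no row for Week 52 in all patients with a Week 52 value.

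The reach is modest. The Week 24 primary and key secondary endpoints and their tests are untouched. What is affected is descriptive: mainly the exploratory Week 52 endpoints, plus immunogenicity and safety by visit.

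The documents support no percentage for the size of any bias. What can be said is that, with one patient of each kind, the 'Week 52' mean shifts by about 1/9 of the completer-versus-off-drug difference for 10 patients, and by about 1/4 for five SBS-IF patients. A favourable direction is plausible for the PS endpoints but is not established.

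**What to change.** In SAP 2.1.1.1:

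1. Define 'Week 52' as Visit 12 data from every FAS patient assessed at the scheduled Week 52 time point, on or off treatment. Do not use a bare ±14-day window: protocol 8.1.7 lets the EoT visit be postponed by up to 8 weeks under COVID-19 measures, and a strict window would lose those visits.
2. Keep 'EOT' for all patients, and show the week of assessment for early withdrawals.
3. If the completer view is wanted, keep it as an extra row labelled as completers.
4. Define completers.
5. Reconcile SAP 4.3.1 with protocol 7.1 on data collected after treatment stops. State when the Visit 12 form is filled in for a patient who stops drug but stays. Without this, the new row may recover nothing.

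Trough concentration needs its own rule. SAP 2.4 sets only a minimum time since the last dose, so an off-drug Week 52 sample would count as a trough unless excluded.

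The cost is a few lines of text and one derived analysis-visit variable, with no new data. The Week 52 figures may come out slightly less favourable.
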